Although EGFR is clearly a good target for HNSCC, we chose to abandon cetuximab-IRDye800 and move forward with another near-infrared fluorescence labeled antibody, panitumumab-IRDye800, because: 1) Panitumumab is a fully humanized anti-EGFR-antibody resulting in fewer infusion reactions (cetuximab Grade 1-2 infusion reactions are as high as 30% (63,64); 2) Panitumumab is a member of the IgG2 subclass of IgG proteins in human serum, which have lower complement activation and low Fc receptor binding, and thus induces minimal inflammation and toxicity; 3) Tumor-to-background ratios obtained with panitumumab-IRDye800 are similar, if not better, than with cetuximab-IRDye800 (65); and 4) Panitumumab displays an improved safety profile; we have only seen one Grade 1 adverse event reported in 37 subjects that were infused with panitumumab-IRDye800 (IRB-35064) compared to 15 Grade 1 adverse events in 12 subjects that were given cetuximab-IRDye800 (NCT01987375). In addition, in the phase 1 cetuximab-IRDye800 study, in 2 subjects the study drug was not given because of an infusion reaction to cetuximab (66,67).

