5.2.1.1 Dermatologic and Soft Tissue Toxicity (Black Box Warning)

In one study, dermatologic toxicities occurred in 90% of subjects and were severe (NCI CTC Grade 3 and higher) in 16% of subjects (package insert). The clinical manifestations included,

but were not limited to, dermatitis acneiform, pruritus, erythema, rash, skin exfoliation, paronychia, dry skin, and skin fissures. Subjects who develop dermatologic or soft tissue toxicities should be monitored for the development of inflammatory or infectious sequelae. Life threatening and fatal infectious complications including necrotizing fasciitis, abscesses, and sepsis have been observed in subjects treated with panitumumab. Panitumumab should be withheld or discontinued for toxicities associated with severe or life-threatening inflammatory or infectious complications.

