5.2.1.5 Hypomagnesemia and Electrolyte Abnormalities

In one study, hypomagnesemia (NCI-CTC Grade 3 or 4) requiring oral or intravenous electrolyte repletion occurred in 2% of subjects. Hypomagnesemia occurred 6 weeks or longer after the initiation of panitumumab (package insert). Both hypomagnesemia and hypocalcemia occurred in some subjects. Electrolytes should be monitored periodically during treatment and for 8 weeks after the completion of therapy when used as anti-cancer treatment. For this study, electrolytes will be monitored for 30 days after administration of panitumumab-IRDye800. Replete electrolytes as necessary using standard infusion guidelines.

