7.5 Safety Monitoring and Reporting

7.5.1. Monitoring and Recording of Adverse Events

Both serious and non-serious AEs will be clearly noted in source documentation and listed on study-specific Case Report Forms (CRFs). The PD or designee will assess each AE to determine whether it is unexpected according to the Informed Consent, Protocol Document, or Investigator's Brochure, and related to the investigation.

All adverse events (AEs), regardless of seriousness or relationship to study drug, are to be collected only on designated study dates from signing of informed consent through 30 days after administration of study drug, and recorded in the study-specific worksheets, with the following exceptions:

- AEs that are solely laboratory values; are not related to the study drug; AND are clinically non-significant may not be collected.

- Non-serious AEs that occur within 30 (+/-7) days after surgical resection of the tumor; are not related to the study drug; are not clinically significant; AND are expected in the post-surgery clinical setting may not be collected.
- SAEs that occur from signing of informed consent to prior to Day 1 may not be collected unless assessed as possibly, probably or definitely related to a study procedure.

All patients enrolled in this study receive surgical intervention in the course of their standard of care. As a consequence of this surgery, patients may experience certain expected and normal adverse events. The following post-operative adverse events will be captured only in the patient's Electronic Health Record (EHR) source documentation and not in the adverse event log. If the adverse event exceeds the grading listed below or occurs outside the post-operative time window, the adverse event will be recorded in the Adverse Event Logs.

- Surgical wound site and associated, expected secondary signs and symptoms, including:
 - CTCAE v5.0 Grade 1 erythema, edema, and pruritis.
 - CTCAE v5.0 Grade 1 pain associated with surgical wound, including headaches – mild pain, little to no limit on adult daily life.
 - CTCAE v5.0 Grade 1 nausea, vomiting, and dysphagia.
 - CTCAE v5.0 Grade 1 weight loss, anemia, and electrolyte abnormalities.
 - CTCAE v.5.0 Grade 2 trismus.

Whenever possible, symptoms should be grouped as single syndrome or diagnosis. The Investigator should specify the date of onset, maximal intensity, corrective therapy given, outcome, and his/her assessment of causality.

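### The EHR-only list of post-operative events in Section 7.5.1 lacks the drug-relation condition of the neighbouring exceptions, so drug-related Grade 1 skin, gastrointestinal and electrolyte events after surgery may be missing from the AE log

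*Combined protocol and SAP*

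**What the plan says.** Section 7.5.1 opens with a general rule: "All adverse events (AEs), regardless of seriousness or relationship to study drug, are to be collected only on designated study dates". Three exceptions follow.

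- The first covers AEs that are laboratory values only. It requires, among other things, that the event be unrelated to study drug.
- The second covers non-serious events within 30 (±7) days of resection. It also requires that the event be unrelated to study drug.
- The third covers serious events before Day 1, and keeps those related to a study procedure.

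A separate paragraph then notes that all patients have standard-of-care surgery and that some events are expected to follow from it. The events it lists go only to the "Electronic Health Record (EHR) source documentation and not in the adverse event log". The list stands under a heading about the wound site and associated expected signs. It includes "CTCAE v5.0 Grade 1 erythema, edema, and pruritis", Grade 1 nausea, vomiting and dysphagia, and "CTCAE v5.0 Grade 1 weight loss, anemia, and electrolyte abnormalities". One item, trismus, is listed at Grade 2. The paragraph gives two routes back to the log: "If the adverse event exceeds the grading listed below or occurs outside the post-operative time window".

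Section 5.2.1.1 gives "dermatitis acneiform, pruritus, erythema, rash, skin exfoliation" among the skin manifestations of panitumumab. Section 5.2.1.5 says of electrolytes: "Both hypomagnesemia and hypocalcemia occurred in some subjects". Section 9.2.6 schedules serum magnesium and phosphorus at Day 15 (±4).

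**The concern.** Two exceptions in the section are written so that a drug-related event cannot fall into them. The EHR-only list is not, and some of its terms are ones the protocol itself names as panitumumab toxicities. A site that applies the list as written would leave a related Grade 1 event out of the log.

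Section 7.5.2 sends non-serious AEs to the FDA annual report and to IRB continuing review. I assume the log is the source for both, although the protocol does not say so. The protocol also argues the agent's safety at Grade 1 level: Section 2.1 says "we have only seen one Grade 1 adverse event reported in 37 subjects", against 15 Grade 1 events in 12 subjects given cetuximab-IRDye800. If this trial of 20 subjects is later summarised in the same way, a few unlogged Grade 1 events would matter to the comparison.

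**Working it through.** The plan gives no figure to reproduce. The check compares the rules and then works out the timing.

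**1. The rules side by side (Section 7.5.1)**

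| Rule | Must be unrelated to study drug? | What returns an event to the log |
|---|---|---|
| General rule | No; collected whatever the relation | Not applicable |
| Laboratory-only exception | Yes | Drug relation, or clinical significance |
| Post-surgery exception | Yes | Drug relation, clinical significance, or not expected after surgery |
| EHR-only list | Not stated | Higher grade, or outside the window |

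**2. A test case: Grade 1 low magnesium at Day 15, judged possibly related**

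- Section 3.2 excludes subjects with low magnesium, so the finding is new since entry and meets the AE definition in Section 7.1.
- General rule: collect.
- Laboratory exception: does not apply, because the event is related. Collect.
- Post-surgery exception: does not apply, for the same reason. Collect.
- EHR-only list: the term is listed, the grade is not exceeded and, if the window is still open, the event stays off the log.

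The last result contradicts the other three. The same steps apply to Grade 1 pruritus, erythema, nausea or vomiting judged related, with the clinical-event exception in place of the laboratory one. Of these, Section 5.2.1 names pruritus and erythema for panitumumab; it does not name nausea or vomiting.

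**3. Timing**

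Inputs: surgery on Day 1 to 5 after infusion (Section 9.1, footnote 8); a window of 30 (±7) days after resection (second exception in 7.5.1); the Day 15 visit at ±4 days (Section 9.2.6). The list does not name its window, so using the second exception's window is an assumption.

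- Earliest close: Day 1 + (30 − 7) = Day 24.
- Latest close: Day 5 + (30 + 7) = Day 42.
- Nominal close: Day 1 + 30 = Day 31, to Day 5 + 30 = Day 35.
- Day 15 visit: 15 − 4 = Day 11, to 15 + 4 = Day 19.

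Day 19 is before Day 24, so the visit always falls inside the window. With the nominal window, 30 − 5 = 25 to 30 − 1 = 29 of the 30 days of AE collection after infusion are post-operative (83% to 97%).

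If the window is something else, the visit lies between 11 − 5 = 6 and 19 − 1 = 18 days after surgery. A window of 18 days or more covers every Day 15 visit, and one shorter than 6 days covers none. The Day 15 draw is the last scheduled magnesium and phosphorus measurement.

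**4. What the rule does not reach**

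- Skin and electrolyte events of Grade 2 or higher are logged, as are events before surgery.
- Rash, dermatitis acneiform, infusion reactions, and pulmonary and ocular toxicities are not on the list.
- A DLT under Section 4.4 needs Grade 2 or greater, so no Grade 1 event can count as one.
- The endpoints in Sections 10 and 12 are diagnostic, and no Grade 1 AE rate is planned for analysis.

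**The case against.** The paragraph introduces its list as consequences of surgery, and the heading speaks of expected secondary signs. Under Section 7.3 even a possibly related event must be unlikely to be explained by the patient's condition or other therapies. An event put down to surgery is therefore not possibly related, and an event judged possibly related is arguably not on the list. The text after the list asks again for a causality assessment. Section 7.5.2 also says abnormal laboratory and clinical assessments go to a CRF, and the EHR is itself source documentation.

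Much of this stands. A reader might infer that the protocol orders related events to be kept off the log regardless of causality, or that panitumumab's named toxicities vanish from the safety record. The documents support neither. The first is an inference from a missing condition. The second ignores the grade limit, the source record and the CRF.

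Few events may be at stake. Section 5.1.1 says the dermatologic toxicities were not associated with single doses. Section 5.2.1.5 places hypomagnesemia at 6 weeks or later, beyond the Day 30 contact. Section 5.2.1 expects mainly infusion or allergic reactions.

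The surgical framing still does not cure the rule. Electrolyte abnormalities, anemia and weight loss are not wound-site findings, so the heading does not clearly confine them. Causality is not among the stated routes back to the log. If the list were meant only for unrelated, expected events, it would largely repeat the second exception. And a CRF entry for an abnormal value is not an AE log entry with grade and causality.

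**Conclusion.** The point holds as a narrow drafting defect that should be corrected. Section 7.5.1 gives conflicting instructions for a drug-related Grade 1 event of a listed type after surgery: the general rule and the first two exceptions keep it, and the EHR-only list removes it. On the assumed window the conflict covers every Day 15 visit and most of the follow-up after infusion. The documents do not allow an estimate of how many events would be lost.

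A reader might also infer that the Grade 1 figures the sponsor already quotes are too low because of this rule. The documents do not support that. One event in 37 subjects (Section 2.1) and one in 55 (Section 5.2.1) come from a different study, and the event in Section 5.2.1 was an elevated QTc, which is not on the list. The consequence is limited to the completeness of this trial's own Grade 1 record. Neither the stopping rule nor any planned diagnostic estimate changes.

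**What to change.** Make two changes in Section 7.5.1.

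1. State that the EHR-only list applies only to events assessed as not related to panitumumab-IRDye800 or Lymphoseek, so that related events of any grade enter the AE log with grade and causality.
2. Define the list's post-operative window in days from resection, or refer explicitly to the window in the second exception.

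Do not go further and require every abnormal magnesium or phosphorus value to be logged. The first exception already exempts laboratory-only values that are unrelated and clinically non-significant, and such a rule would create a new conflict.

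The cost is a short amendment, a few more log entries and a slightly higher reported count of Grade 1 AEs. No procedure or treatment changes.

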7.5.2. Reporting Adverse Events and Serious Adverse Events

Non-serious adverse events will be reported annually to FDA via an Annual Report (IND 119474) and to IRB via Continuing Review.

The PD (aka Principle Investigator) must immediately report within 24 hours of knowledge of event to the Sponsor (ie, IND Holder, [name]), any serious adverse event, whether or not considered related to study drug. SAEs of all grades will be reported to the Sponsor using the Stanford Cancer Institute SAE CRF. The investigator must provide a detailed description of the event, the treatment regimen, relevant laboratory and evaluations and assessment of the relationship of the AE to the study drug. All relevant information should be reported as it becomes available.

SAEs CTCAE Grade 3 and above, and all subsequent follow-up reports will be reported to the Stanford Cancer Institute Data and Safety Monitoring Committee (DSMC) using the study specific CRF regardless of the event's relatedness to the investigation. Following review by the DSMC, events meeting the IRB definition of an "Unanticipated Problem" (UP) will be reported

to the IRB using eProtocol within 10 working days of DSMC review, or within 5 working days for deaths or life-threatening experiences.

Adverse events deemed serious, unexpected (ie, not described in the protocol, Investigator's Brochure or informed consent documents) and related to study drug must be reported to Sponsor using the FDA MedWatch form 3500a within 24 hours of knowledge of event. The Sponsor is responsible for deciding whether the event meets IND Safety Reporting criteria.

Events will be submitted to Sponsor [name], at:

[name]
Professor of Otolaryngology-Head and Neck Surgery & Radiology		
[name]
[name]
[name]
[contact]		94305

It will be the responsibility of the Sponsor to provide to the FDA all information concerning significant hazards, contraindications, side effects or precautions felt significant to the safety of the drug being studied. The PD is responsible for accurate and timely communication to the Sponsor of any events reportable to FDA. Subjects will be instructed prior to participation on the importance of reporting any symptoms (new or worsening), and/or any physical changes throughout their participation in the study. These events will be recorded accordingly in the CRF. Abnormal laboratory and/or clinical assessments will also be captured in the appropriate CRF.

8. CORRELATIVE/SPECIAL STUDIES

Confirm our phase 1 study in HNSCC (IRB-35064), we will continue collecting pharmacokinetics data, hence the blood draws. We will also continue collecting imaging data on the primary tumor. This data will be used for: 1) drug delivery studies to gain better insight in the panitumumab-IRdye800 distribution in the tumor (including, but not limited to, photoacoustic imaging); and 2) to further study if the drug can be used to define (intraoperative) margins. Furthermore preoperative standard of care imaging obtained during routine evaluation will be used to correlate with pathological findings.

9. STUDY CALENDAR

9.1 Study Procedures Table

Enrolled subjects will follow schedule of evaluations provided below:

	Screening/ Pre-treatment (≤ 30 days before treatment)	Day 0	Day 0 to 4	Day of Surgery (Day 1 to 5)	Day of discharge ¹²	Day 15 (±4 days ¹²)	Day 30 (±4 days)
Informed Consent	X						
Medical History	X						
Physical Examination¹	X	X			X	X	
Vital Signs	X	X	X	X	X	X	
Height and weight	X	X					
Performance Status¹	X				X	X	
ECG	X²						
Chemistries³	X	X		X		X	
Hematology⁴	X					X	
Serum pregnancy¹¹	X	X¹¹					
PK - fluorescent-labeled antibody⁵		X	X⁵	X	X	X	
PK – Immunogenicity⁶		X				X	
IV infusion of Panitumumab-IRdye800⁷	X						
Local administration of Lymphoseek¹³			X				
Sentinel node mapping (lymphoscintigraphy + SPECT/CT imaging)¹³			X				
Surgical Resection				X⁸			
Tumor imaging				X⁹			
Pathological evaluations¹⁰				X			
Adverse events¹⁵		X	X	X		X	X
Concurrent medications¹⁴	X	X	X	X		X	X

1. A physical examination and performance status assessment will be done at screening; Day 0; Day of discharge; and Day 15. Examinations collected for surgical procedure are acceptable for screening purposes. Examinations do not have to be repeated on Day 0 if completed within 21 days of infusion.
2. ECG will be obtained at screening to evaluate baseline. A previous ECG that was obtained as part of standard of care may be used as the screening ECG as long as it was obtained within 21 days of infusion.
3. Chemistries to include a standard basic metabolic profile with magnesium and phosphorus. Chemistries and other blood work collected for surgical procedure are acceptable for screening purposes. Chemistries do not have to be repeated on Day 0 if completed within 21 days of infusion. On Day of Surgery and Day 15 only magnesium and phosphorus are collected.
4. Hematology (ie, CBC W/O DIFF) values include WBC; RBC; Hgb; hematocrit and platelet counts. Blood work collected for surgical procedure are acceptable for screening purposes.

5. Serum level of panitumumab-IRDye800 will be drawn on Day 0 prior to dose and 30 (\pm 10) minutes after the end of infusion, on Day 1 if applicable, day of surgery, up to once a day on Days 1, 2, and 3 post-operative as available, Day of discharge, and Day 15 to assess circulating fluorescent-labeled antibody and unconjugated dye.
6. Blood will be obtained pre-infusion and 15 days after infusion and banked for future immunogenicity testing. Immunogenicity testing time points will not vary with dose.
7. Infusion of study drug to be given over 15 (\pm 5) minutes followed by a 30 (\pm 10) minute observation period.
8. Surgical excision occurs 1 to 5 days after the panitumumab-IRDye800 infusion based on subject availability/scheduling.
9. Tumors will be imaged intraoperatively using the devices listed in Appendix B to determine threshold of detection.
10. All resected tissues will be evaluated for near-infrared fluorescence (NIR) fluorescence prior to and after pathological examination.
11. Serum pregnancy test will be obtained on all women of childbearing age at screening; a urine pregnancy test will be performed on Day 0 if the result of a serum pregnancy test within 72 hours before administration of panitumumab-IRDye800 is not available.
12. Blood will also be obtained as needed to evaluate any abnormal lab values experienced after study drug infusion. Blood will not be taken at Day of Discharge if it is within the window of their Day 15 visit.
13. Lymphoseek will be administered locally on the day before surgery. Directly after injection, lymphoscintigraphy will be performed to identify the drainage pattern of the tracer and to identify hot spots (ie, sentinel nodes). SPECT/CT imaging will be performed to determine the anatomical location of the hot spots.
14. Concurrent medications will be reported at screening, Day 0 and Day 15, and in-between if any medication is given to treat adverse events or serious adverse events that in the assessment of the PI are possibly, probably or definitely related to a study procedure.
15. See Section 7.5.1 for adverse events monitoring and reporting.

9.2 Study Procedures

The following evaluations and procedures will be performed:

9.2.1 Screening/Pre-Treatment (Within 30 days of treatment start)

- Obtain written informed consent
- Medical history including current medications
- Physical examination
- Performance Status
- ECG
- Vital signs (blood pressure, heart rate, respiratory rate, temperature)
- Height and weight
- Chemistries (standard basic metabolic profile with magnesium and phosphorus)
- CBC and platelets
- Serum pregnancy test for women of childbearing potential
- Assessment for concomitant medications
- Collect data from any standard-of-care information, including, but not limited to MRI, and PET/CT, performed prior to surgery

9.2.2 Day 0

- **Prior to Infusion of panitumumab-IRDye800**
 - Physical Examination (within 21 days)
 - Performance Status (within 21 days)

- Vital signs (blood pressure, heart rate, respiratory rate, temperature)
- Chemistries (standard basic metabolic profile with magnesium and phosphorus, within 21 days)
 - (may skip if previous assessment within 14 days)
- Pregnancy test for women of childbearing potential - a urine pregnancy test will be performed on Day 0 if the result of a serum pregnancy test within 72 hours before administration of panitumumab-IRDye800 is not available
- Blood sample for panitumumab-IRDye800 antibody pharmacokinetics
- Blood sample for future assessment of immunogenicity
- **IV infusion of panitumumab-IRDye800 over 15 (\pm 5) minutes**
 - Vital signs immediately following panitumumab-IRDye800 infusion (+ 5 mins) (blood pressure; heart rate; respiratory rate; temperature)
- **Observation for 30 (\pm 10) minutes**
- **At the end of the observation period (ie, 30 (\pm 10) minutes after the end of panitumumab-IRDye800 infusion)**
 - Vital signs (blood pressure, heart rate, respiratory rate, temperature)
 - Blood sample for panitumumab-IRDye800 antibody pharmacokinetics
 - Assessment for concomitant medications
 - Assessment for adverse events

9.2.3 Day 0 to -4 (Day before Surgery) – for Cohort 1 only

- Vital signs (blood pressure, heart rate, respiratory rate, temperature)
- Blood sample for panitumumab-IRDye800 antibody pharmacokinetics
- Local Lymphoseek injection
- Preoperative LN mapping using lymphoscintigraphy and SPECT/CT imaging
- Assessment for adverse events
- Assessment for concomitant medications

9.2.4 Day 1 to 5 (Day of Surgery)

- Vital signs prior to surgery (blood pressure, heart rate, respiratory rate, temperature)
- Serum magnesium and phosphorus
- Blood sample for panitumumab-IRDye800 antibody pharmacokinetics
- Scheduled routine surgical resection based on standard-of-care histopathology
- Intraoperative imaging (fluorescence signal detection)
- Intraoperative gamma tracing (radioactive signal detection) (Cohort 1 only)

- Pathological evaluations – tissue assessments of the pathological tissues by optical scanning after clinical assessment by pathologist but prior to permanent fixation of the tissue
- Assessment for adverse events
- Assessment for concomitant medication

